### 9.7.2. Sensor Glucose Values

SG data will be collected by subject's study pump and calibrated by subject's Accu-Chek™\* Guide Link study meter.

### 9.7.3. HbA1c

Collected at screening for exclusion criteria.

### 9.7.4. Blood Ketone Values

Blood ketones will be measured by all subjects using the FreeStyle Optium Neo ketone meter when certain conditions are met. The control solution test will be performed following the manufacturer's user guide. The investigational center staff will be trained on the use of the FreeStyle Optium Neo ketone meter per the manufacturer's instructions. All ketone measurements will be entered by study subjects into the Log Book section of the CareLink™ software.

Note: In the event the blood ketone meter is not used by subjects to collect ketone values, urine ketones should be measured and entered appropriately into the CareLink™ software as urine ketones.

## 9.8. Recording Data

Data will be captured on eCRFs using Oracle Clinical Remote Data Capture's (OC-RDC) module. Original eCRFs will not be considered as source data and supporting documentation will be required. The food log and subject questionnaires on paper are considered source data, then source data is transferred to an eCRF.

Electronic device data will be collected from the study pump using CareLink™ software. The system uses TLS technology, which encrypts all data it stores (21 CFR Part 11 compliant). Certain data points stored in the downloaded information may also be captured on the appropriate eCRF. These data files will be sent to the sponsor electronically using the internet and a secure cloud-based site (Box).

Laboratory results will be recorded on eCRFs.

The investigator will ensure that all eCRFs are completed promptly, completely, and accurately. Medtronic will provide detailed instructions to assist with eCRF completion. In the event of data discrepancies, investigational centers will be asked to resolve queries electronically in the OC-RDC system; otherwise, irresolvable data-related issues will be routed to the sponsor for review and final disposition. An audit trail is maintained in OC-RDC to capture any corrections or changes of the eCRFs. System backups for data stored in the Oracle Clinical system will be consistent with Medtronic Standard Operating Procedures (SOPs).

Medtronic will only consider eCRFs to be complete when all discrepancies between source data and eCRF have been resolved and eCRF content has been reviewed by the study monitor. In addition, specific eCRFs must also be reviewed and electronically signed by the investigator, indicating his/her agreement with the accuracy of all recorded data. It is expected that the investigator and his/her staff will cooperate with the monitoring team and provide any missing data in a timely manner.

## 9.9. Deviation Handling

A deviation is any instance(s) of failure to follow, intentionally or unintentionally, the requirements of the CIP. It is expected that the investigator will conduct this clinical trial in compliance with the CIP and all applicable regulations governing the conduct of clinical research involving human subjects. Failure to do so could result in one or all of the following:

- Investigational center disqualification
- Notification to the regulatory authorities/EC depending on the severity of the deviation and reporting requirements

The investigator should not implement any deviation from, or changes to, the CIP without agreement by the sponsor and prior review and documented approval/favorable opinion from the EC, except where necessary to eliminate an immediate hazard(s) to trial subjects, or when the the change does not affect the scientific soundness of the plan or the rights, safety, and welfare of the subjects.

### Deviations related to instructions provided to study subjects :

As subjects may not follow the instructions perfectly (e.g. SMBG, system use, sensor use, etc.), no study deviation will be given unless the site staff did not train the subject appropriately.

### 9.9.1. Documenting Requirements for Study Deviations

#### 9.9.1.1. Unplanned CIP Deviations

The investigator may encounter the need to deviate from the CIP when necessary to protect the safety, rights or well-being of a subject in an emergency or in unforeseen situations beyond the investigator's control (e.g. subject failure to attend scheduled follow-up visits, inadvertent loss of data due to computer malfunction, inability to perform required procedures due to subject illness).

All deviations from the CIP, regardless of the reason should be documented as soon as possible, after deviation occurs or is identified. This documentation should include deviation date, description of the deviation, corrective action and the reason for deviation.

CIP deviations should be reported as follows:

- a) To the EC for notification/acknowledgement,
- b) To the sponsor and, if required;
- c) To the regulatory agency, if required

#### **9.9.1.2. Minor or Administrative CIP Deviations**

Minor or administrative deviations are those that do not "affect the scientific soundness of the research plan or the rights, safety, or welfare of human subjects."

Deviations that do not meet the criteria for expedited notification or prior regulatory/EC approval, may be reported at the time of eCRF completion or separately upon discovery such as during monitoring visits.

If a CIP deviation occurs which meets this definition, the deviation should be reported to the EC at the time the continuing review application is submitted.

#### **9.9.2. Reporting Requirements for Study Deviations**

All study deviations must be reported on the eCRF regardless of whether medically justifiable, an inadvertent occurrence, or taken to protect the subject in an emergency. Any deviations from the CIP will be documented in the clinical study report.

In order to protect the rights and interests, safety and health of subjects, the deviation occurred under emergency situations that cannot be timely reported shall be reported in written form afterwards in accordance with relevant regulations as soon as possible.

The following examples are deviations that could impact subject safety, affect the integrity of study data and/or affect subject's willingness to participate in the study. These deviations are significant and require immediate sponsor notification upon investigator awareness.:

- Failure to obtain informed consent and assent (if applicable), i.e., there is no documentation of informed consent
- Informed consent and assent (if applicable) obtained after initiation of study procedures
- Continued study participation of a subject who did not meet all inclusion/exclusion criteria
- Performing study procedure not approved by the EC
- Failure to inform EC and sponsor of reportable AEs (see Section 11.4)

- Investigational study device dispensed without obtaining informed consent and assent (if applicable)

Reporting of all other study deviations should comply with EC policies and/or local laws and must be reported to Medtronic as soon as possible upon the center becoming aware of the deviation. Reporting of deviations must comply with EC policies, local laws, and/or regulatory agency requirements. Refer to Investigator Reports, Table 6 for specific deviation reporting requirements and timeframes for reporting to Medtronic, EC, and/or regulatory agency (if applicable).

### 9.9.3. Analyzing Deviations

Medtronic is responsible for reviewing deviations, assessing their significance, and identifying any additional corrective and/or preventive actions (e.g. amend the CIP, conduct additional training, terminate the investigation). Repetitive or serious investigator compliance issues may result in initiation of a corrective action plan with the investigator and investigational center, and in some cases, necessitate suspending enrollment until the problem is resolved or ultimately terminating the investigator's participation in the study.

## 9.10. Subject Withdrawal or Discontinuation

Subjects may choose to withdraw from the study at any time by notifying investigational center staff of their intent.

If a subject chooses to end his or her study participation or if the subject is removed from the study at the investigator's discretion or for failure to meet the study requirements, the reason for withdrawal must be documented. All study devices and supplies must be returned (as applicable) and documented both in source documents and on an eCRF.

Subjects may also be withdrawn from the study at the discretion of the investigator. A subject may be withdrawn from the study if:

- In the opinion of the investigator, the subject's health or safety would be compromised by continuing in the study
- In the opinion of the investigator, it is in the subject's best interest to discontinue participation in the study
- The subject is found to no longer meet all inclusion criteria, or is found to meet one or more exclusion criteria
- The subject fails to comply with one or more study requirements
- The subject is lost to follow up
- During the course of the study, subject begins participation in another investigational study (drug or device).
- During the course of the study, subject begins abusing illicit drugs.
- During the course of the study, subject begins abusing alcohol.

- During the course of the study, subject begins using pramlintide (Symlin), DPP-4 inhibitors, liraglutide (Victoza or other GLP-1 agonists), metformin, canagliflozin (Invokana or other SGLT2 inhibitors).
- During the course of the study, subject receives red blood cell transfusion or erythropoietin.
- During the course of the study, the subject demonstrates that he/she is not able to comprehend instructions for study procedures, as evaluated by the appropriate research staff.
- During the course of the study, subject is taking oral, injectable, or IV glucocorticoids
- During the study, (female) subject becomes pregnant.
- During the study, the subject experiences one severe hypoglycemic episode
- During the study, the subject experiences one episode of DKA
- During the study, subject has a cardiovascular event or any vascular event such as stroke.

## Lost to Follow-up

In the case that the subject is determined to be lost to follow-up, details of a minimum of two attempts and the method of attempt (e.g., one letter and one phone record or two letters) to contact the subject must be recorded. In addition, the requirements set by the governing EC for subjects lost to follow-up must be followed.

Documentation of the reason(s) leading to subject withdrawal will be kept in the subject's source documentation.

Upon exiting from the study, no further study data will be collected or study visits will occur for the subject. All data available through the time of the subject's exit will be used for analysis. In the event of study exit, the investigator should discuss with the subject the plans for future care and treatment. The investigator should explain that the subject will continue to receive standard medical care. Alternative treatment, such as medication options or follow-up through standard of care procedures instead of study procedures, and medical consequences should also be discussed. Source documentation of this conversation recommended. The investigator must notify the subject of any significant new findings that may become available during the course of the study, which are pertinent to the safety and well-being of the subject.

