## 5. Objectives and Endpoints

### 5.1. Objectives

#### 5.1.1. Primary Objective(s)

To evaluate the safety, effectiveness and usability of the Medtronic MiniMed™ 670G system in Chinese patients with type 1 diabetes.

*Medtronic Confidential*

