**5.2.5. Subject Feedback**

Descriptive summary will be used to characterize study questionnaire(s) results.

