## 9. Study Procedures

### 9.1. Study Timeline

#### Visit Schedule:

#### **Run-in Period Visits: To be completed approximately up to 35 days**

[figure not shown]
- Visit 1: Screening (Office):
  - Consent
  - Collect demographic and baseline characteristics:
    - Age
    - Gender
    - Race
    - Ethnicity
    - Height and Weight
  - Obtain prior Medical History
  - Collect concomitant medications
  - Labs (pregnancy test [if applicable], HbA1c, TSH, Hct, GA and eGFR)
  - Screening Requirements
- Visit 2: Run-in Period Start - Visit 2 (Office): 2 - 7 days after Visit 1
  - ***Eligibility has been confirmed including labs***
  - **All eligible subjects:**
    - Start study pump; provide pump training
    - Collect questionnaire(s)
    - Collect information about food consumed in last 24 hours (food log)
  - Subjects who are using pump **with** CGM at Screening:
    - Visits 2 and 3 may be combined
    - Start CGM, provide CGM training
    - Start CGM run-in (2 weeks)
    - Install Mobile App to Smartphone (if applicable)
    - System is set Manual Mode (Sensor Augmented Pump only):  

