# CIP329 Clinical Investigation Plan

10939060DOC

Version C

Page 49 of 99

Medtronic

	Run-in Period				Study Period			
	Visit 1 (O)	Visit 2 (O)	Visit 3 (O)	Visit 4 (O)	Visit 5,6 and 7 (O/T)	Visit 8 and 9 (O/T)	Visit 10 (O)	Visit 11 (O)
O= Office T= Telephone								
Provide subjects with study reference materials. Review EZ reference guide		x						
Disburse the MiniMed™ 670G pump		x						
Start study pump		x						
• SmartGuard™ features remain turned OFF								
Disburse the Guardian Link (3) transmitter		x (as applicable)	x					
Disburse Guardian Sensor (3) sensors		x (as applicable)	x				x	x
Disburse the Study Meter		x						
Disburse the Ketone Meter		x						
Disburse the Blue adapter		x						
Disburse study supplies as needed		x	x	x	As needed	As needed	x	x
Instruct subjects to have access to oral glucose, oral carbohydrates or glucagon and instruct subjects to keep these supplies available at all times (as needed)		x						
Adjust pump settings as needed:		x	x	x	As needed	As needed	As needed	As needed
• Determine carbohydrate to insulin ratios (may differ by mealtime)								
• Adjust active insulin time								
• Adjust basal rate settings for time periods spent in Manual Mode								
• Adjust insulin sensitivity as needed								
Install Mobile App on subject's Smartphone (if applicable)		x	x					
Collect general HCL training information from training checklist (e.g., MiniMed™ 670G system features and training time)		x	x	x				
Collect/Assist with the Questionnaires		x						x
Schedule the next visit date and time	x	x	x	x	x	x	x	x

*Medtronic Confidential*

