### **16.11.2. Subject Follow-Up In Case of Termination**

In case of early investigational center suspension or termination, all subjects should be contacted to plan an early Termination visit at the investigational center. All efforts will be made to complete and report all study observations at the time of termination. The subject will return the study devices to the investigational center (unless subject is allowed to keep them per country requirement), receive appropriate treatment and follow-up.

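### Questionnaire feedback on Auto Mode comes from completers only, because the sole questionnaire after Visit 4 is at Visit 12 and none is scheduled at early withdrawal

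*Protocol*

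**What the plan says.** The primary objective (Protocol 5.1.1, repeated in SAP 4.1.1) is: "To evaluate the safety, effectiveness and usability of the Medtronic MiniMed™ 670G system in Chinese patients with type 1 diabetes". No endpoint is labelled a usability endpoint. The nearest item is Subject Feedback (Protocol 5.2.5 and 14.9, SAP 7.9.5): "Descriptive summary will be used to characterize study questionnaire(s) results". SAP 7.11 says much the same. None of these sections gives a population or a denominator.

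Protocol 9.1 puts questionnaires at Visit 2, when the study pump is started in Manual Mode, and at Visit 12, which is 30 days after Visit 4 (±3 days) and ends the study. In Table 3 the row "Collect/Assist with the Questionnaires" agrees: one mark at Visit 2 and one at the last visit. Auto Mode is turned on at Visit 4. Table 3 has no early-exit column.

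On withdrawal, Protocol 9.10 (Lost to Follow-up) says: "Upon exiting from the study, no further study data will be collected or study visits will occur for the subject". The next sentence is: "All data available through the time of the subject's exit will be used for analysis". For subjects who leave or are removed, 9.10 also says: "All study devices and supplies must be returned (as applicable) and documented both in source documents and on an eCRF". When a whole centre is suspended or closed, Protocol 16.11.2 asks for an early termination visit and adds: "All efforts will be made to complete and report all study observations at the time of termination". Protocol 14.5 rules out imputation. SAP 7.4 does so for device data and does not mention questionnaires.

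**The concern.** A subject who starts Auto Mode and leaves before Visit 12 is never asked, by questionnaire, what the closed-loop system was like to use. Some of the reasons for leaving in Protocol 9.10 may bear on usability: failure to comply with study requirements, inability to comprehend the procedures, an episode of severe hypoglycemia or DKA, or the subject's own choice. If such subjects would have rated the system lower than those who stayed, the descriptive summary is too favourable. It bears on one of the three named parts of the primary objective, in a study meant to support registration. The loss cannot be repaired at analysis, because the answers are never collected.

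**Working it through.** **1. Which questionnaire can describe Auto Mode?** Visit 2 comes before Visit 4, so its answers cannot. Visit 12 is the only later occasion (Protocol 9.1, Table 3).

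**2. What happens to a subject who exits between Visit 4 and Visit 12?** No questionnaire is scheduled at individual exit, and none can follow it under 9.10. The rule that data up to exit are analysed does not help, because no Auto Mode questionnaire exists by then.

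**3. What else is collected up to exit?** Device deficiencies run from consent to study end (Protocol 5.2.4), and their definition in Section 13 includes use errors. Subjects are asked about device performance at every visit from Visit 2 (Table 3). Auto Mode time is a secondary endpoint from device data (Protocol 14.6.2). Leavers contribute to all three.

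**4. The plan's own figure.** The 50 completers come from the power statement in Protocol 14.4: difference 5.3, SD 13.0, one-sided alpha 0.025. The noncentrality is 5.3/13.0 × √50 = 2.88. Power is 80.7% from the noncentral t distribution and 82.2% by normal approximation, so the stated figure of more than 80% reproduces. Questionnaire data do not enter this test.

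**5. How many starters would lack the rating?** The number starting Auto Mode is not given. It is assumed here, with 50 completers who all answer at Visit 12.

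| Start Auto Mode (assumed) | Complete | No rating | Share of starters |
|---|---|---|---|
| 55 | 50 | 5 | 5/55 = 9.1% |
| 60 | 50 | 10 | 10/60 = 16.7% |
| 65 | 50 | 15 | 15/65 = 23.1% |
| 70 | 50 | 20 | 20/70 = 28.6% |

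**6. How far could the summary move?** Reported rate minus rate over all starters = share missing × (completers' rate − leavers' rate). Suppose 90% of completers (45 of 50) are favourable, and 80% down to 40% of leavers would have been, a difference of 10 to 50 points. Both rates are assumptions.

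- 55 starters: 9.1% × 10 = 0.9 points, up to 9.1% × 50 = 4.5 points. Over all starters the rate is 89.1% down to 85.5%.
- 70 starters: 28.6% × 10 = 2.9 points, up to 28.6% × 50 = 14.3 points. Over all starters the rate is 87.1% down to 75.7%.

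With no assumption about leavers, the limits are 45/55 = 81.8% to 50/55 = 90.9% with 55 starters, and 45/70 = 64.3% to 65/70 = 92.9% with 70. The upper limits exceed 90%, so the direction of any bias is not fixed by the design.

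**The case against.** The strongest reply is that the documents never designate the questionnaire as the usability measure and do not show its content. Use errors, device-performance reports, calls to technical support and Auto Mode time all reach the analysis for leavers up to exit, and reasons for discontinuation are summarised. This stands. A reader might infer that usability as a whole is measured in completers only; the documents do not support that. What remains is narrower: those sources record faults, use errors and exposure, and none is a questionnaire rating of Auto Mode by the subject.

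A reader might also take 9.10 as forbidding an exit questionnaire. It forbids data after exit; before exit it simply schedules none.

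A third tempting reading is that one third of subjects, (75 − 50)/75 = 33%, lose the rating. Protocol 8.2 counts a subject as enrolled at consent, so the 75 includes screen failures and run-in exits who never used Auto Mode. They belong in neither the numerator nor the denominator.

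Bias is possible, not certain. Several withdrawal reasons, such as pregnancy, glucocorticoid use or joining another study, need have nothing to do with usability. The pivotal trial described in Protocol 4.1.2 saw no severe hypoglycemia or DKA in 12,389 patient-days, so withdrawals for those events may be few.

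Finally, a device-return contact is not guaranteed. The return rule carries a qualifier and names no visit, Protocol 7.8.4 provides for missing devices, and subjects lost to follow-up may have no contact. The contrast with centre closure is only suggestive, since 16.11.2 does not name questionnaires. These points limit what a remedy can recover but do not remove the gap.

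**Conclusion.** The point holds for questionnaire feedback on Auto Mode: under the schedule as written it can come only from subjects who reach Visit 12. For 55 to 70 assumed starters with 50 completers, 9% to 29% of starters would have no rating. The illustrative overstatement runs from about 1 to about 14 percentage points, resting on assumed satisfaction rates for an instrument whose content is not given. If more than 50 complete for a given number of starters, the missing share is smaller.

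The consequence is confined to a descriptive summary. Success is judged on time in range alone (Protocol 14.6.1, SAP 7.9.1), and that test, its alpha and its power are untouched. The change is still worth making, because the summary bears on a named part of the primary objective and the missing answers cannot be recovered later.

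**What to change.** **Protocol 9.10 and Table 3.** State that any subject who exits after Visit 4 is asked to complete the Visit 12 questionnaire at the exit or device-return contact, in person or by telephone, before exit is recorded. Add an early-exit entry to the questionnaire row. Subjects who leave during run-in need not be asked, since they have not used Auto Mode.

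**SAP 7.9.5 and 7.11.** Report the number answering out of all subjects who started the study period (the ITT population in SAP 7.1.3). Show completers and early leavers separately, and list reasons for non-response.

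**Cost.** One sentence and one table entry in the protocol, and one sentence in the SAP. The questionnaire already exists, and neither the sample size nor the primary analysis changes. Some leavers will decline or be unreachable, so the gap will shrink rather than close; the reported denominator will show how much remains.

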## 9.11. Stopping Rules

### 9.11.1. Subject Stopping Rules

Any event of DKA or severe hypoglycemia will result in withdrawal of subject from study.

### 9.11.2. Stopping Rules for Entire Study

During the study period, the following steps will be taken for:

- Unanticipated Adverse Device Effects (UADE)
  - Device related Diabetic Ketoacidosis (DKA)
  - Device related Severe hypoglycemia
1. Site will notify the sponsor within approximately 24 hours of receiving knowledge of the event.
  2. CEC is to review and adjudicate the event.
  3. CEC will provide recommendation to the sponsor on the following:
    - a) If enrollment and the study may continue
    - b) If enrollment should be stopped, while already enrolled subjects are allowed to continue in study
    - c) If the entire study must be stopped, including subjects who have already received study devices.

